## **4.2. Final Analyses**

An analysis will take place when the total number of events (280 PFS events/deaths) is reached in the study. An event is defined as when a subject has disease progression (PD) or death due to any cause during the study. All available data will be analyzed and the results will be presented in a report. Released data that are available from later visits will also be included.

An additional analysis will take place after all subjects have completed follow-up or have been withdrawn from the study.

## **5. SAMPLE SIZE CONSIDERATIONS**

### **5.1. Sample Size Assumptions**

The primary objective of this study is to evaluate progression-free survival (PFS) of ofatumumab maintenance treatment vs. no further treatment after remission induction in patients with relapsed CLL as determined by investigator assessment based on NCI-WG CLL criteria [Hallek, 2008]. The sample size calculation is based on the primary endpoint, PFS, using the following assumptions and was calculated using East 5.3 software:

- Exponential survival curves where the ratio of the hazard rates is constant over Time
- Median PFS for the no further treatment group is 28 months (based on REACH, Robak, et al, 2008)
- Median PFS for the ofatumumab maintenance treatment group is 39.2 months (40% improvement over the no further treatment group)

- A 1:1 stratified randomization scheme
- A 5% two-sided risk of erroneously claiming a difference in the presence of no true underlying difference (alpha level)
- An 80% chance of successfully declaring a difference in the presence of a true underlying difference (power)
- Accrual rate of 12 subjects per month
- Stratified Log-rank test for hypothesis testing

Using the above assumptions, approximately 280 total events from both treatment arms are needed for the study to attain 80% power. With a total sample size of 478 evaluable subjects, the total duration of the study will be approximately 63.5 months in order to obtain the 280 total events. Assuming a dropout rate of 10%, the total sample size for both arms combined will be about 532 and the total duration of the study will be approximately 68 months.

As the significance level was met at the interim efficacy analysis, further enrollment in the study will be discontinued. There will be no changes to the study design, treatment, assessments, or follow-up.

**5.2. Sample Size Sensitivity**

The robustness and sensitivity of the above sample size calculation is considered in order to assess the impact on power should the assumed median PFS vary in the ofatumumab maintenance group. The following table shows the estimated power for different median values of PFS for the ofatumumab maintenance group. The total number of events is 280, and the total number of evaluable subjects is 478.

Median PFS (months) for Ofatumumab Maintenance	Median PFS (months) for No Further Treatment	Estimated Power
35	28	0.47
36.4	28	0.60
39.2	28	0.80
42	28	0.92

**5.3. Sample Size Re-estimation**

Sample size re-estimation is not planned for this study.

## **6. ANALYSIS POPULATIONS**

### **6.1. Intent-to-Treat Population**

The Intent-to-Treat (ITT) population will include subjects who are randomized in the study. This will be the primary population used for evaluation of the efficacy data for all efficacy assessments. In the analyses, subjects will be grouped based on how they are randomized regardless of which treatment they receive. The ITT population will also be used for all PRO analyses.

### **6.2. Safety Population**

The Safety population will include all randomized subjects. This population will be used for evaluation of all safety measurements. In the analyses, subjects will be grouped based on the treatment they received regardless of how they are randomized.

### **6.3. Per Protocol Population**

The Per-Protocol (PP) population will comprise all randomized subjects and will exclude subjects with major protocol deviations that will impact the efficacy outcome. The Per Protocol Population will be used in the primary endpoint analysis to check the robustness of the results when using the ITT population. However, if the difference between the ITT and the Per-Protocol population is 10% or less, then the Per-Protocol analysis will not be performed.

Subjects who meet the following conditions will be considered as major protocol violators:

- Failure to be a PR or CR at study entry
- Received only 1 or more than 3 previous induction treatments
- Failure to demonstrate diagnosis of CLL
- Failure to satisfy the following inclusion criteria: The anti-leukemia treatment before study entry should have been for at least 3 months or 3 cycles.
- Received previous autologous or allogeneic stem cell transplantation (exclusion criteria)
- Had know transformation of CLL (e.g., Richter's transformation), prolymphocytic leukemia (PLL) or CNS involvement of CLL (exclusion criteria)
- Received prohibited therapies or procedures for CLL

### **6.4. Pharmacokinetic Population**

The Pharmacokinetic Population will consist of all subjects in the ITT population for whom a pharmacokinetic sample is obtained and analyzed.

## 6.5. Analysis Datasets

The primary data set for efficacy will be based on the investigator response assessments. The primary data sets for safety will be based on the adverse events and the laboratory data.

The responses will be assessed by the investigators and changes in response will be determined according to the IWCLL updated NCI-WG CLL criteria (Hallek, 2008). Data will be summarized for investigator assessed response, and statistical inference for efficacy claims will also be based on investigator assessed response data.

## 7. TREATMENT COMPARISONS

The primary treatment comparison of interest will be ofatumumab maintenance treatment vs. no further treatment. The primary comparison will be based on progression-free survival (PFS) when the total number of events reaches 280 in the ITT population.

The primary efficacy endpoint will serve as gatekeeper for the interpretation of treatment comparisons for the ‘inferential’ secondary endpoints. If  $H_0$  is rejected at the 0.001 significance level at the planned interim analysis, the conclusion will be that there is a treatment difference between ofatumumab maintenance treatment and no further treatment, and the p-values for the ‘inferential’ secondary endpoints may be interpreted and tested at the 0.05 significance level for the final analysis. If  $H_0$  is not rejected at the interim or final analysis, the conclusion will be that there is no difference between ofatumumab maintenance treatment and the no further treatment arm, and all other p-values will be used for descriptive [REDACTED] purposes only.

The following endpoints are considered as ‘inferential secondary endpoints’ and will be tested and compared between the ofatumumab maintenance treatment and the no further treatment group if the primary endpoint, PFS, is significant.

1. Time to next CLL therapy
2. Overall survival

To control for multiplicity across the ‘inferential secondary endpoints’, the test of  $H_0$  will be performed in a sequential manner to control the type I error at 0.05 as follows:

- 1- Time to next CLL therapy
- 2- Overall survival

For the primary efficacy endpoint and the inferential secondary endpoints, any p-values for the comparison of ofatumumab maintenance treatment vs no further treatment that achieve statistical significance under multiplicity adjustment will be identified in the study report as inferentially significant for confirmatory purposes.

Any other comparisons of interest between the ofatumumab maintenance treatment and the no further treatment arms for other secondary endpoints will be done at an alpha level equal to 0.05. No multiplicity will be considered in the other secondary endpoints and any p-value that is  $\leq 0.05$  will be identified as nominally significant.

## 7.1. Data Display Treatment and Other Subgroup Descriptors

For all tabulations, Ofatumumab Maintenance and Observation (no further treatment) will be presented.

All listings will be presented by individual treatment arm.

If the sample size permits, the stratification factors will be used for subgroup analyses. The stratification factors include: CR or PR at study entry; number of previous induction treatments (2 vs 3); and type of prior treatment (chemoimmunotherapy, only alkylating monotherapy, or other treatment).

The following treatment descriptors will be used on all applicable displays:

Treatment Group		Data Display	Order of Treatment Groups
Code	Description		
A	Ofatumumab Maintenance	Ofatumumab	1 st treatment column
B	Observation	Observation	2 nd treatment column

## 8. GENERAL CONSIDERATIONS FOR DATA ANALYSES

Analysis datasets will be created according to CDISC/ADaM standards, and data will be listed and summarized according to GSK Integrated Data Standards Library (IDSL) reporting standards. Formatting for dates, times, and decimal places will follow GSK standards except where specified.

The currently supported version of SAS will be used to perform all data analyses and to generate tables, listings, and figures. All data in the database will be presented in subject data listings. Data displays will follow the agreements proposed by the IDSL where possible.

Unless otherwise stated, continuous variables will be summarized with the following statistics: mean, median, standard deviation, minimum, and maximum. Categorical variables will be summarized with frequency counts and percentages.

All data up to the time of study completion/withdrawal from study will be included in the analysis, regardless of duration of treatment

All confidence intervals will be two-sided and will use a 95% confidence level.

Deviations from the analyses in the RAP will be identified in the CSR.

## 8.1. Multicenter Studies

Data from all participating centers will be pooled prior to analysis. It is anticipated that subject accrual will be spread thinly across centers and summaries of data by center would not be informative and will not be provided. However, a summary of enrollment by center will be provided.

## 8.2. Other Strata and Covariates

In all efficacy analyses, the tests will be stratified by the baseline stratification factors: (1) CR or PR at study entry, (2) number of previous induction treatments (2 vs 3) and (3) type of prior treatment : chemoimmunotherapy, only alkylating monotherapy, or other treatment. The demographic summaries will document the number of subjects who fall into each stratum for the ITT population. PFS, the primary endpoint, will also be summarized according to the stratification factors.

Subjects will be considered to fall into the respective stratification categories according to the actual data given in the eCRF. Hence, if any misallocations took place in the stratification, it will be the actual data which will be used to determine the stratification of the subject rather than the data as recorded on RAMOS.

In addition to stratification factors, treatment arm as well as age, gender and race will be considered as covariates in the Cox regression model to assess the effect of ofatumumab maintenance treatment vs. no further treatment.

## 8.3. Examination of Subgroups

Summary tables for PFS will be provided by the baseline stratification factors: (1) CR or PR at study entry, (2) number of previous induction treatments and (3) type of prior treatment : chemoimmunotherapy, only alkylating monotherapy, or other treatment.

Other subgroups of interest include may include age (<70 vs ≥70), gender, race RAI/Binet Stage, ECOG (0-1 vs 2), baseline cytogenetics, cytogenetics at relapse, prognostic factors (Beta-2 microglobulin, IgVh status) , baseline lymphocyte count and MRD status.

## 8.4. Multiple Comparisons and Multiplicity

The primary efficacy endpoint will serve as gatekeeper for the interpretation of treatment comparisons for the ‘inferential’ secondary endpoints. If  $H_0$  is rejected at the 0.001 significance level at the planned interim analysis, the conclusion will be that there is a treatment difference between ofatumumab maintenance treatment and no further treatment, and the p-values for the ‘inferential’ secondary endpoints may be interpreted and tested at the 0.05 significance level for the final analysis. If  $H_0$  is not rejected at the interim or final analysis, the conclusion will be that there is no difference between ofatumumab maintenance treatment and the no further treatment arm, and all other p-values will be used for descriptive and [REDACTED] purposes only.

The following endpoints are considered as ‘inferential secondary endpoints’ and will be tested and compared between the ofatumumab maintenance treatment and the no further treatment group if the primary endpoint, PFS, is significant.

1. Time to next CLL therapy
2. Overall survival

To control for multiplicity across the ‘inferential secondary endpoints’, the test of  $H_0$  will be performed in a sequential manner to control the type I error at 0.05 as follows:

- 1- Time to next CLL therapy
- 2- Overall survival

For the primary efficacy endpoint and the inferential secondary endpoints, any p-values for the comparison of ofatumumab maintenance treatment vs no further treatment that achieve statistical significance under multiplicity adjustment will be identified in the study report as inferentially significant for confirmatory purposes.

Any other comparisons of interest between the ofatumumab maintenance treatment and the no further treatment arms for other secondary endpoints will be done at an alpha level equal to 0.05. No multiplicity will be considered in the other secondary endpoints and any p-value that is  $\leq 0.05$  will be identified as nominally significant.

## **9. DATA HANDLING CONVENTIONS**

### **9.1. Premature Withdrawal and Missing Data**

#### **Withdrawal**

Subjects will be observed until study completion or study withdrawal due to unacceptable adverse events(s), consent withdrawal or other reasons. All data up to time of withdrawal will be included in the analysis.

Subjects who are withdrawn prematurely from study treatment but who are not withdrawn from the study at the time of the analysis will be included in the analysis, regardless of treatment duration.

#### **Missing Data**

Missing data occurs when any requested data is not provided, leading to blank fields on the collection instrument. This data will be indicated by the use of a “blank” in subject listing displays. Answers such as “Not applicable” and “Not evaluable” are not considered to be missing data and should be displayed as such.

Since the period of follow-up for any subject will be dependent on efficacy and toxicity, the duration of follow-up will vary among subjects. Consequently, there will be no imputation for missing data. Randomized subjects who do not have any response data will be assumed to be non-responders and will be censored at the date associated with the last visit.

For the PFS endpoint, subjects who are alive and have not progressed at the time of analysis will be censored at the date associated with the last visit with an adequate assessment. If a progression event occurs after an extensive lost-to-follow-up time (more than 2.5 assessment windows), the primary analysis will censor those subjects at the last date of their last visit with an adequate assessment even if subsequent information is available regarding progression or date of death.

Subjects with the designation of treatment relationship for adverse events (AE)s and serious adverse events (SAEs) missing will have the worst case assumed to impute the relationship: if relationship to study treatment is missing it will be assumed to be “Yes”.

There will be no other imputation for missing data other than what’s described in Section 9.2 for partial dates and for missing exposure end dates.

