## **12. SAFETY ANALYSES**

Unless otherwise specified, all the safety analyses will be based on the Safety population as defined in Section 6 and summaries will include all events or assessments collected during the study. All the analyses will be performed by treatment arm.

The list of displays for the Safety Analyses is shown in a separate document from the RAP.

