In addition, the frequency and percentage of AEs (all grades) will be summarized and displayed in two ways: 1) in descending order of total incidence by PT only and 2) in descending order of total incidence by System Organ Classes (SOC) and PT. In the SOC row, the number of subjects with multiple events under the same system organ class will be counted once.

A separate summary will be provided for study treatment-related AEs. A study treatment-related AE is defined as an AE for which the investigator classifies the relationship to study treatment as “Yes”. A worst case scenario approach will be taken to handle missing relatedness data, i.e. the summary table will include events with the relationship to study treatment as ‘Yes’ or missing. The summary table will be displayed in descending order of total incidence by PT only.

All AEs will be listed. Additionally, a listing of subject IDs for each individual AE will be produced.

Adverse events will be summarized and listed separately during the study and up to 60 days after the last dosing.

The following adverse event tables will also be provided for events occurring from the

start of treatment until 60 days after last dosing:

- All adverse events, all serious adverse events (including deaths) for the following:
  - Secondary malignancies
  - Cardiac events
  - Small bowel Obstruction
- All infusion reactions reported as AEs, SAEs and leading to withdrawal
- All infections reported as adverse events, all serious infections reported as adverse events
- All mucocutaneous adverse events, all serious mucocutaneous adverse events
- All decreased neutrophil count/ hemoglobin count/ and platelet count adverse events, all serious decreased neutrophil count/ hemoglobin count/ and platelet count adverse events
- All autoimmune hematologic complication adverse events, all serious autoimmune hematologic complication adverse events
- All tumor lysis syndrome adverse events, all serious tumor lysis syndrome adverse events

The relationship between MedDRA SOC, PT, and Verbatim will be displayed.

Summaries based on the following covariates will be provided for all AEs:

- Gender
- Age: <70 vs. ≥70 years
- Race: White, vs. non-white.

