#### **12.4. Deaths and Serious Adverse Events**

In the event that a subject has withdrawn consent, no data after the withdrawal of consent date from this subject including death is supposed to appear in the database, which should be part of the data cleaning process. All deaths will be summarised based on the number and percentage of subjects. This summary will classify subjects by time of death relative to the last dose of medication (>60 days or ≤60 days) and primary cause of death (disease under study, SAE related to study treatment, or other). A supportive listing will be generated to provide subject-specific details on subjects who died.

All SAEs will be tabulated based on the number and percentage of subjects who experienced the event. SAEs will be summarized up to 60 days after last infusion. Separate summaries will also be provided for study treatment-related SAEs, fatal SAEs and study treatment related fatal SAEs. The summary tables will be displayed in descending order of total incidence OR incidence by PT only.

A study treatment-related SAE is defined as an SAE for which the investigator classifies the relationship to study treatment as “Yes”. A worst case scenario approach will be taken to handle missing data, i.e. the summary table will include events with the relationship to study treatment as ‘Yes’ or missing.

SAEs are included in the listing of all adverse events. Separate supportive listings with subject-level details will be generated for

- Fatal SAEs
- Non-Fatal SAEs.

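### Blank adverse-event causality is imputed as treatment-related without limiting the rule to subjects who received ofatumumab

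*SAP*

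**What the plan says.** SAP 9.1 (Missing Data) gives the rule for AEs and SAEs: subjects with no recorded relationship "will have the worst case assumed to impute the relationship: if relationship to study treatment is missing it will be assumed to be" 'Yes'. The same section treats a field as missing when requested data are left blank. It adds that answers such as 'Not applicable' and 'Not evaluable' "are not considered to be missing data and should be displayed as such".

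The rule returns in two places. For related AEs, SAP 12.2 states: "A worst case scenario approach will be taken to handle missing relatedness data", and "the summary table will include events with the relationship to study treatment as" 'Yes' or missing. For related SAEs, SAP 12.4 states: "A worst case scenario approach will be taken to handle missing data", with the same 'Yes' or missing criterion. Neither section mentions treatment arm or exposure, and neither repeats the 'Not applicable' exception.

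These sections decide whom the rule reaches:

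- SAP 6.2: "The Safety population will include all randomized subjects", grouped by treatment received.
- SAP 12: "All the analyses will be performed by treatment arm".
- SAP 7.1: tabulations carry an ofatumumab and an observation column.
- SAP 12.2: AEs and SAEs are collected in the observation arm over a matching period.
- SAP 9.2.1: observation subjects receive no treatment.

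**The concern.** A worst-case rule for causality is conservative when the subject has had the drug. For a subject who never had it, an imputed 'Yes' cannot be correct. The rule as written has no exposure condition, so it would produce that false value whenever an observation subject's relationship field is blank.

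The outputs concerned are the AE overview counts of related AEs, related SAEs and related fatal SAEs (SAP 12.2), and the drug-related tables in Appendix 1 of the 280-event plan: 3.0181, 3.0280 to 3.0310, 3.0360 to 3.0411, 3.0450 to 3.0451, 3.0510 to 3.0540, and 3.0590 to 3.0600. None of these titles is limited to one arm. At stake is a non-zero observation entry in tables where the only valid entry is zero or not applicable, read side by side with the ofatumumab column.

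The rule also carries forward. The 280-event plan (Section 1) keeps the interim data rules. The final-analysis plan (Section 1) keeps the previous conventions and lists most of the drug-related tables again.

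**Working it through.** The plan states no figure on this point, so there is none to reproduce.

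**Does the rule reach the observation arm?** Observation subjects are in the Safety population (6.2), their AEs are collected (12.2), and they have a column in the tables (7.1, 12). The imputation carries no exposure condition (9.1, 12.2, 12.4). A blank relationship field in that arm is therefore set to 'Yes'. A 'Not applicable' answer is not, by the definition in 9.1. The rule can reach the arm; whether it does depends on how the field is completed, which the documents do not say.

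**Effect on the between-arm difference.** Let pO and pC be the proportions with an AE on ofatumumab and observation, r the truly related share of pO, and mO and mC the proportions of those subjects with missing causality, unrelated to the true answer. This is a subject-level simplification.

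- True difference: pO·r
- Rule as written: ofatumumab = pO[r + (1 − r)mO]; observation = pC·mC
- Ofatumumab-only rule: same ofatumumab value; observation = 0
- Missing counted as unrelated: pO·r(1 − mO); observation = 0

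Against the ofatumumab-only rule, the difference falls by exactly pC·mC. Against the true difference, it falls only if pC·mC > pO(1 − r)mO.

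**Illustration.** The documents give no AE, relatedness or missingness rates, so all of these are assumed: pO = 0.85, pC = 0.75, r = 0.30. Arm size is 478/2 = 239, from the planned evaluable number and 1:1 allocation.

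Inflation of the observation column, pC·mC:

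- mC = 0%: 0 points, 0 subjects
- mC = 1%: 0.75 points, about 2 subjects (0.0075 × 239 = 1.8)
- mC = 5%: 3.75 points, about 9 subjects
- mC = 10%: 7.5 points, about 18 subjects

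Difference under the rule as written, against a true difference of 0.85 × 0.30 = 25.5 points:

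- mO = mC = 5%: 0.85 × (0.30 + 0.70 × 0.05) − 0.75 × 0.05 = 28.5 − 3.75 = 24.7 points
- mO = 1%, mC = 10%: 26.1 − 7.5 = 18.6 points
- mO = 5%, mC = 0: 28.5 points, larger than the truth
- Field blank for the whole observation arm (mO = 0, mC = 100%): 25.5 − 75.0 = −49.5 points, a reversed sign

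For comparison, counting missing as unrelated at mO = 5% gives 0.85 × 0.30 × 0.95 = 24.2 points. That is slightly below the 24.7 from the rule as written with 5% missing in both arms.

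**A second way to see the size.** Assume 5 AEs per observation subject and independent blanks with probability q per event. The chance of at least one false 'related' AE is 1 − (1 − q)^5: 0% at q = 0, 4.9% at q = 1%, 9.6% at q = 2%, and 22.6% at q = 5%.

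**The case against.** The best defence is the definition in SAP 9.1 itself. If the eCRF does not request the relationship field for observation subjects, or records 'Not applicable', the rule never applies to them. The eCRF is not in the documents. SAP 9.2 leaves derivations to separate dataset specifications, and Protocol Section 7 requires data cleaning. This stands: it makes zero a possible answer and rules out any claim that the arm is known to be affected. It does not repair the text, because the correctness of the tables then rests on a convention the SAP never states.

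A reader might infer that blank is the natural entry for an untreated subject. Nothing in the documents supports that. A reader might also infer that the rule must shrink the true ofatumumab excess. It need not, because it raises the ofatumumab count too; with 5% missing on ofatumumab only, the illustrated difference grows.

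The consequence is also limited. The SAP specifies no between-arm test of drug-related events, and the explicitly comparative safety tables (3.1282, 3.1283) are not titled as drug-related. A non-zero entry in an untreated column would be a visible anomaly, since all AEs are listed.

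The contrast with infusion-reaction tables, which are titled for the ofatumumab arm only, is weak evidence of oversight: those events require an infusion. Better evidence is that the SAP adapts other rules for the untreated arm, namely reference date (9.2.1), baseline (9.2.7) and study periods (9.3), but not this one.

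**Conclusion.** The gap is real and narrow. As written, SAP 9.1, 12.2 and 12.4 give a false value every time the imputation applies to a subject who never received ofatumumab. That is more than missing detail, because the stated rule is wrong for that arm.

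The number of subjects affected is unknown and may be zero. The 0 to 7.5 point range rests on an assumed 75% AE rate and 0% to 10% subject-level missingness. The 0% to 22.6% range rests on an assumed five AEs per subject, independent blanks and 0% to 5% missing per event. The sign reversal requires the field to be blank for the entire observation arm, which nothing in the documents indicates.

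A reduced between-arm difference is certain only in comparison with an ofatumumab-only rule, and only if some observation fields are blank.

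The effect is confined to relatedness summaries. All-causality AE, SAE and death tables, PFS, overall survival and time to next therapy are untouched.

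**What to change.** In SAP 9.1, 12.2 and 12.4, and in the final-analysis plan that inherits them:

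1. Apply 'missing = Yes' only to subjects who received at least one dose of ofatumumab. This fits the as-treated grouping in 6.2 and keeps the conservative handling of ofatumumab events.
2. Show the observation column of drug-related tables as not applicable. This preserves the two-column layout of 7.1.
3. Report the number of relationships imputed, and state how the eCRF records the field for observation subjects.
4. Footnote any difference from the interim CSR tables.

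The cost is one sentence, a filter in the related-event programs and the footnote. No new data are needed. The one real drawback is some loss of consistency with tables already reported, which the footnote covers.
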